8.6 Leukapheresis

Collection of PBMCs via leukapheresis will be performed in accordance with the standard practices of the participating apheresis center. Typically, in this procedure, approximately 3 liters of blood will be processed using peripheral veins for venous access. The blood will be anticoagulated in accordance with standard practice of the apheresis center.

Postprocedural safety assessments will be performed in accordance with the standard practices of the participating apheresis center. Additionally, the participant will be advised to contact the study site if they experience any AEs following the procedure.

Eligibility for leukapheresis:

- Prior to leukapheresis, participant must meet all apheresis center requirements for this procedure
- Participants who can become pregnant must have a negative urine pregnancy test within 48 hours prior to the procedure

8.7 Visit procedures, schedule, windows, and missed visits

The schedules of visits and evaluations performed at each visit are shown in Appendix A (for participants undergoing lymph node FNA) and Appendix B (for participants not undergoing lymph node FNA). Visit windows are shown in Appendix C. The procedures for documenting missed visits and out-of-window visits are described in the HVTN 305 Study-specific Procedures (SSP). If the missed visit is one that required safety assessments or local safety labs, HVTN CRS staff should attempt to bring the participant in for an interim visit as soon as possible.

8.8 Monitoring for acquisition of HIV

Study participants will be tested for presence of HIV periodically throughout the study, as indicated in the schedules included in Appendix A and Appendix B. The Laboratory Program (or approved diagnostic laboratory) will follow the HVTN HIV testing algorithm (see HVTN Laboratory Center Manual of Procedures (MOP), which is able to distinguish vaccine-induced Ab responses from the presence of actual HIV. Participants will be promptly informed and counseled if they acquire HIV during the study and will be referred for treatment (see Section 5.2.2).

Study participants will receive regularly scheduled counseling regarding avoidance of HIV acquisition in accordance with the most recent Centers for Disease Control and Prevention HIV-counseling guidelines.

Although the study vaccine will not cause HIV acquisition, it may induce Abs detectable by standard HIV screening techniques. This is referred to as vaccine-induced seropositivity (VISP). The following steps will be taken to protect participants from adverse consequences associated with VISP:

 Participants will be counseled to avoid HIV Ab testing outside of the HVTN CRS during study participation.

- Participants can receive HIV diagnostic testing from the CRS following their last scheduled visit until they are told they do not have VISP.
- Participants with VISP will be periodically offered free-of-charge poststudy HIV diagnostic testing (per the HVTN poststudy HIV testing algorithm) as medically/socially indicated (approximately every 6 months) unless or until HIV Ab testing is no longer standard in clinical settings.
- Unless participants request that their names be removed, the names of all participants in HVTN studies are entered into a secure VISP registry in order to verify that an individual received an HIV vaccine (and therefore has the potential for VISP) and to qualify former participants for poststudy HIV testing to distinguish between VISP and HIV acquisition. Information in the VISP registry is not used for research.

8.9 Early termination visit

If a participant terminates participation in the study early for any reason, the site PI should consider if the following assessments are appropriate: end-of-study HIV test, CBC with differential, serum chemistry (ALT and creatinine), physical examination, social-impact assessment, and, if indicated, a pregnancy test (see Appendix A and Appendix B). For participants living with HIV, please see Section 5.2.2. If the site PI has questions regarding a termination visit, they should consult with the PSRT.

8.10 AESI contact

CRS staff will contact study participants at month 18 to collect the information listed below and will ask an abbreviated set of EP-injection-site related skin changes and tolerability assessment questions that can be conducted over the phone. If indicated, the participant may be asked to come in for a clinical assessment, which may also include referrals for an AESI assessment. AESIs are described further in Appendix I.

- Confirmation of vital status; if deceased, attempt to learn cause and date of death
- If participant is alive, record the participant's responses to the following:

SAEs, EAEs;

AESIs (a sample list of AESI is provided in Appendix I). AESIs are reported regardless of relationship to study product(s);

Medically attended adverse events (MAAEs), defined as any AE leading to an unscheduled visit to a healthcare professional. MAAEs are reported regardless of relationship to study product(s);

New diagnosis of HIV acquisition; and

Pregnancies and outcomes, including congenital anomalies/birth defects.

All such events will be recorded and AEs will be assessed for relationship to study vaccines.

9 Safety and AEs

9.1 AEs

AEs will be collected over a period of 30 days after each vaccination. All collected AEs are captured in the clinical database on the appropriate CRF. Clinic staff should evaluate every AE to determine if (1) the AE meets the requirements for expedited reporting (see Section 9.2.1), (2) the AE meets the criteria for a safety pause/prompt AE review (see Section 9.6), (3) the AE meets the criteria for an MAAE, and (4) the AE is a potential immune-mediated disease that may be listed as an AESI. A sample list of AESIs is provided in Appendix I.

In addition, a limited set of AEs will be collected and reported until (but not including) the month 18 visit:

- SAEs/expedited adverse events (EAEs),
- AESIs,
- MAAEs, and
- AEs leading to early participant withdrawal or early discontinuation of study vaccine(s) administration.

AEs will be graded according to the DAIDS Table for Grading the Severity of Adult and Pediatric Adverse Events, Corrected Version 2.1 (https://rsc.niaid.nih.gov/clinical-research-sites/daids-adverse-event-grading-tables), with the following exceptions:

- Unintentional weight loss is required to be reported as an AE only if it is considered to be potentially deleterious to the participant's health (see HVTN 305 SSP).
- Do not grade creatinine clearance or estimated glomerular filtration rate (eGFR) based on the change from the baseline parameter. Do not grade on the basis of eGFR if there is clinical concern for acute kidney injury.
- Injection-site erythema or redness and injection-site induration or swelling will not consider surface area and interference with usual social and functional activities, such that:

Grade 1 is: 2.5 to < 5 cm in diameter;

Grade 2 is: > 5 to < 10 cm in diameter;

Grade 3 is: ≥ 10 cm in diameter OR ulceration OR secondary infection OR phlebitis OR sterile abscess OR drainage;

Grade 4 is: potentially life-threatening consequences (eg, abscess, exfoliative dermatitis, necrosis involving dermis or deeper tissue).

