3.1 Primary objectives and endpoints

Objectives	Endpoints
1) To evaluate the safety and tolerability of 3 doses of sD-NP-GT8 + IL-12 DNA adjuvant with or without 2	 a) Local and systemic reactogenicity signs and symptoms will be collected for a minimum of 2 weeks following receipt of any study vaccine b) SAEs, medically attended adverse events (MAAEs), AESIs,
doses of Trimer 4571 + 3M- 052-AF/Alum adjuvant	and AEs leading to early participant withdrawal or permanent discontinuation will be collected throughout the study and for 12 months following any receipt of study products. Additionally, all AEs will be collected for 30 days after any receipt of study vaccination.
2) To evaluate the immunogenicity of 3 doses of sD-NP-GT8 + IL-12 DNA adjuvant with or	a) Response rate and magnitude of HIV-1–specific binding Ab responses to eOD-GT8-60mer, eOD-GT8 monomer, or Trimer 4571 as assessed by multiplex assay 2 weeks following the third (Groups 1 and 2) and fourth (Group 3) vaccinations
without 2 doses of Trimer 4571 + 3M-052-AF/Alum adjuvant	b) Response rate and magnitude of CD4+ and CD8+ T-cell responses, measured by flow cytometry, to HIV-1–specific Env peptide pools 2 weeks following the third (Groups 1 and 2) and fourth (Group 3) vaccinations
3) To evaluate the induction of VRC01-class B cells	a) Frequency of VRC01-class B cells from lymph nodes and periphery following the second and third vaccinations

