Appendix A Schedule of procedures: Participants undergoing FNA

	Number	01	02	03	04	05	06	07	08	09	10	11	12	AESI ¹⁸
Stud		0	2	4	6	7	12	14	15	24	26	52	78	
Study		0	0.5	1	1.5	1.75	3	3.5	3.75	6	6.5	12	18	
	udy Day	-56 to 0	1	15	29	43	50	85	99	106	169	183	365	547
	ocedure	Screen ¹	Vac 1		Vac 2		FNA	Vac 3		FNA	Vac 4 ¹⁷			
Study procedures														
Assessment of Understanding		√												
Informed consent		√												
Medical history ²		√												
Physical exam ³		√	√	√	√	√		√	√		√	√	√	
Contraception status assessment ⁴		√	√		√			√			√			
Social impact assessment			√	√	√	√		√	√		√	√	√	
Social impact questionnaire					√			√					√	
Risk-reduction counseling ⁵		√	√	√	√	√		√	√		√	√	√	
Concomitant medications ⁶		√	√	√	√	$\sqrt{7}$	√	√	$\sqrt{7}$	√	√	√	V	
Adverse Events (AEs)			√	√	√	√		√	√		√	√		
AESIs/MAAEs/SAEs			√	√	√	√		√	√		√	√	V	√
Vaccination ⁸			√		√			√			√			
Reactogenicity assessment ⁹			√		√			√			√			
EP injection site assessment				√	√	√	√	√	√	√	√	V	√	$\sqrt{18}$
Clinical labs	Tube													
Pregnancy test (urine or serum) 10,11		√	√		√		√	√	√	√	√			
HBsAg/anti-HCV ¹¹	SST	5												
HIV screening test ^{11,12}	SST	5												
Calcium ¹¹	SST	5												
CBC/Differential ¹¹	EDTA	5		5		5			5			5		
ALT & Creatinine ¹¹	SST	5		5		5			5			5		
HIV diagnostic test	EDTA							10				10	20	
Research samples ¹³														
PBMC for assays & storage	ACD			42.5		136		13614				136	178.5	
Serum for assays and storage	SST	34		34		34			34			34	34	
Leukapheresis ¹⁵		√							√					
Fine Needle Aspiration ¹⁶							√			√				
Daily volu	me (mL)	59	0	86.5	0	180	0	146	44	0	0	190	232.5	
56-day total volu				145.5	145.5	325.5	325.5	326	370	370	0	190	232.5	

Green shading: Vaccination visit for all groups; **Blue shading:** Vaccination visit for Group 3 only.

- ¹ Screening evaluations at Visit 01 are performed no more than 56 days before Day 1.
- ² Medical history: A complete medical history is performed during screening. At enrollment and at subsequent visits, an interim medical history may be performed.
- ³ A complete **physical exam** is performed at screening and last clinic visit to include height, weight, and vital signs, and clinical assessments of head, ears, eyes, nose, and throat; neck and lymph nodes; heart; chest; abdomen; extremities; neurological function; and skin. At other visits, a **targeted physical exam** will be performed as needed, based on participant reports or indications of illness

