- ¹⁷ Vaccination 4/Visit 10 will be conducted only for participants assigned to Group 3.
- ¹⁸ **AESI contact:** CRS staff will contact study participants at month 18 to collect the information listed in Section 8.10. The EP-injection–site assessment will be an abbreviated questionnaire that can be conducted over phone.

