Appendix C Visit windows

Visit #	Visit Type	Lower allowable window (-)	Lower target window (-)	Target day*	Upper target window (+)	Upper allowable window (+)up
01	Screening Leukapheresis	-56	-	0	-	+0
02	Enrollment / Vaccination 1	-	-	1	-	-
03	2 weeks postvaccination 1	-	-4	15	+4	+7
04	Vaccination 2	-	-	29	+9	+28
05	2 weeks postvaccination 2	-	-4	43	+4	+7
06*	FNA postvaccination 2	-	-4	50	+4	+10
07	Vaccination 3	-	-	85	+14	+28
08	2 weeks postvaccination 3 Leukapheresis Primary immunogenicity	-	-4	99	+4	+7
09*	FNA postvaccination 3	-	-4	106	+4	+10
10	Vaccination 4 (Group 3 only)	-	-7	169	+14	+28
11	2 weeks postvaccination 4 for Group 3; follow-up visit for Groups 1 and 2	-	-4	183	+4	+7
12	Final clinic visit	-28	-14	365	+14	+28
AESI**	AESI contact	-21	-14	547	+14	+28

All target dates are relative to Day 1, with the exception of visits, 3, 5, 8, and 11 (for Group 3 only) which are relative to the vaccination immediately preceding the visit.

^{*}Visits 06 and 09 are only applicable to participants providing lymph node FNA collections. The FNA visits are relative to the preceding vaccination.

^{**}This contact must be at least 12 months post last vaccination

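### In Group 3, the 30-day all-AE window after vaccination 4 extends past the last visit scheduled to ask about all adverse events

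*Protocol*

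**What the plan says.** The primary safety endpoint in Protocol Section 3.1 states that "all AEs will be collected for 30 days after any receipt of study vaccination". SAP Section 3.1 repeats it. Section 9.1 of the Protocol makes it an operating rule: "AEs will be collected over a period of 30 days after each vaccination". Section 9.1 then lists separately a smaller set to be collected for longer: SAEs/EAEs, AESIs, MAAEs, and AEs leading to withdrawal or to stopping study vaccine.

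The schedules in Appendix A (FNA) and Appendix B (no FNA) have two matching rows. The all-AE row is ticked at Visits 2, 3, 4, 5, 7, 8, 10 and 11, and is blank at Visit 12 and at the month 18 contact. The row for AESIs, MAAEs and SAEs is ticked at the same visits and also at Visit 12 and the month 18 contact.

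The footnotes state that "Vaccination 4/Visit 10 will be conducted only for participants assigned to Group 3". Appendix C describes Visit 11 as "2 weeks postvaccination 4 for Group 3; follow-up visit for Groups 1 and 2". In Group 3 it times that visit from the preceding vaccination, with a target window of 4 days either side and an upper allowable limit of +7 days.

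**The concern.** The endpoint promises complete AE collection for 30 days after every dose, but the schedule appears to treat complete collection as finished at Visit 11, two weeks after the last dose. No visit or contact is scheduled between Day 183 and Day 365, and what is scheduled from Day 365 on asks only about the smaller set.

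The events at risk are non-serious AEs for which the participant did not seek care. They feed the SAP tables of AEs by preferred term, severity and relationship. Some could also matter for oversight: under Section 9.6, a related Grade 3 or 4 AE (with listed exceptions) goes to prompt safety review even if it is not serious, and that depends on the site hearing of it.

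The dose concerned is the second of Trimer 4571 with 3M-052-AF/Alum. Table 2-2 of the Protocol lists earlier Trimer 4571 experience with Alum alone. A low AE count late in this window could be read as good tolerability when the schedule never asked.

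**Working it through.** **Inputs.** Vaccination days 1, 29, 85 and, for Group 3 only, 169 (Table 1-1, Appendix C). Window length 30 days (Sections 3.1 and 9.1). AE-ticked visits: Days 1, 15, 29, 43, 85, 99, 169 (Group 3 only) and 183 (Appendices A and B). Visit 12 is on Day 365.

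**Plan's own figure.** Visit 11 minus vaccination 4 = 183 − 169 = 14 days, which agrees with the two weeks in Appendix C.

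**Coverage of each window.** Window end = vaccination day + 30. The window is covered if an AE-ticked visit falls on or after that day.

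| Vaccination | Window end | First AE-ticked visit on or after the end |
|---|---|---|
| 1 (Day 1) | Day 31 | Visit 5, Day 43 |
| 2 (Day 29) | Day 59 | Visit 7, Day 85 |
| 3 (Day 85) | Day 115 | Visit 10, Day 169 (Group 3); Visit 11, Day 183 (Groups 1 and 2) |
| 4 (Day 169, Group 3) | Day 199 | None |

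**Size of the gap after vaccination 4.** If Visit 11 takes place p = 14 + offset days after vaccination 4, the unprompted part is 30 − p days.

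| Visit 11 offset | p | Unprompted days | Length |
|---|---|---|---|
| −4 (lower target) | 10 | 11–30 | 20 (67%) |
| 0 (target) | 14 | 15–30 | 16 (53%) |
| +4 (upper target) | 18 | 19–30 | 12 (40%) |
| +7 (upper allowable) | 21 | 22–30 | 9 (30%) |

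Appendix C gives no lower allowable limit for Visit 11, so −4 is taken as the earliest timing. Because Visit 11 is anchored to the actual vaccination in Group 3, a late vaccination 4 moves both dates and leaves the gap unchanged.

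**Share of the trial.** Planned vaccination visits: 9×3 + 18×3 + 18×4 = 27 + 54 + 72 = 153. The gap follows 18 of these (18/153 = 12%), all in Group 3.

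**Could other procedures fill it?** Group 3 diaries run for 14 full days after vaccination 4 (Section 8.3). Interim history after screening is optional (Appendix A and B footnotes). The month 18 contact covers SAEs/EAEs, AESIs, MAAEs, HIV diagnosis and pregnancy (Section 8.10). Weekly safety-team review is assured only to two weeks after the last injection (Section 9.3.1). None of these is a scheduled prompt for new AEs of every kind on days 15 to 30.

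**The case against.** The best reply is that a tick marks a scheduled prompt and does not limit what is collected. Section 9.1 still obliges sites to record any AE in the 30 days that they learn of. SAEs, AESIs, MAAEs and AEs leading to discontinuation are collected for longer. Unresolved reactogenicity is followed to resolution, and Visit 12 includes a complete physical examination and a concomitant-medication check. All of this stands. It limits the problem to possible under-recording of non-serious events without medical attention. A reader might infer that such events would simply be lost, and the documents do not support that.

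A reader might also infer that the 30-day window fails throughout the trial. It does not: the windows after vaccinations 1 to 3 each have a later AE-ticked visit. Recall after vaccination 3 is long. Events on Days 100–115 are first asked about 54–69 days later in Group 3 (169 − 115 to 169 − 100) and 68–83 days later in Groups 1 and 2 (183 − 115 to 183 − 100). But the plan sets no maximum recall interval, so this is only a secondary observation.

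Nor do the documents support reading the gap as biasing a Group 2 versus Group 3 safety test. That contrast in Section 6.1.1 concerns immune responses. Safety data are tabulated descriptively (Protocol Section 6.4.3, SAP Section 9.2) and set against historical controls (Protocol Section 6.1.2). Group 2 has no vaccination 4, so it has no matching window.

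Finally, the study-specific procedures, which are not part of these documents, may already contain a day-30 contact. That cannot be ruled out; the Protocol and SAP do not name one.

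**Conclusion.** The point holds for one window in one group. For Group 3 (planned 18 of 45 participants), the stated 30-day all-AE window after vaccination 4 has no scheduled prompt for its last 16 days at target timing, or its last 9 to 20 days over the Visit 11 windows. No timing shown in Appendix C closes it. The likely consequence is under-recording of non-serious AEs without medical attention in the descriptive tables, of unknown amount. The documents give no AE rate from which to estimate a number of events.

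This assumes that the blank at Visit 12 is deliberate, that −4 days is the earliest Visit 11, and that no unseen operational document adds a contact. It is a modest inconsistency, but it sits in a primary endpoint and is cheap to correct.

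**What to change.** Reconcile Section 9.1 with Appendices A, B and C. Add one remote contact for Group 3, at or just after day 30 following the actual vaccination 4 date, that asks about all AEs since Visit 11. Section 8.2 already allows remote visits. Give it a row in Appendix C anchored to vaccination 4, with no allowance before day 30.

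As a fallback when that contact is missed, tick the AE row at Visit 12 for Group 3, with a look-back limited to day 30 after vaccination 4. This should not be the main remedy: at target timing, events on Days 184–199 would be asked about 166 to 181 days later (365 − 199 and 365 − 184). If the study-specific procedures already provide a day-30 contact, a cross-reference in the appendices is enough.

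Adding AE ticks at Visits 6 and 9 is not recommended. Only FNA participants attend them, so ascertainment would differ by FNA status, and both come before vaccination 4.

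Cost: one short call per Group 3 participant (18 planned) and edits to three appendices.

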8.3 Reactogenicity assessments

Reactogenicity definition: Signs and symptoms considered to represent reactogenicity from the vaccine include systemic events of increased body temperature, fatigue, generalized myalgia, generalized arthralgia, headache, chills, nausea, and local events at the injection site, including pain/tenderness, induration, and erythema.

The reactogenicity assessment period is the day of vaccination and 7 full days following vaccine administration for INO-6172 alone and 14 full days following vaccine administration for INO-6172 along with Trimer 4571 adjuvanted with 3M-052-AF/Alum and Trimer 4571 alone, adjuvanted with 3M-052-AF/Alum. Clinicians will follow and collect resolution information for any reactogenicity signs and symptoms that have not resolved within the reactogenicity assessment period.

Prevaccine administration: Medical history and evaluations, including vital signs and planned injection-site evaluations, are performed as described in Appendix A and Appendix B

Postvaccine administration in-clinic evaluation: Following the first vaccine administration of sD-NP-GT8, participants will be observed for a minimum of 60 minutes postadministration. For all subsequent injections, participants will be observed for a minimum of 30 minutes with the following exception: for Group 3, participants will be observed for 60 minutes postadministration of Trimer 4571 + 3M-052-AF + Alum. During this time, vital signs will be recorded, the injection site will be inspected for evidence of local reaction, and any evidence of systemic symptoms will be assessed.

Postvaccine administration contact with participant: Remote or in-person contact between the participant and the site staff should take place at least once on the third or fourth day following vaccination. Any postvaccination reaction that is Grade 2 or higher will be assessed by a clinician within 48 hours after onset unless the reaction is improving and/or has completely resolved. Additionally, other clinical concerns may prompt a study visit based on the judgment of a study clinician.

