Guidance for participants scheduling licensed vaccines or allergy treatments: In order to prevent interference with reactogenicity assessments, participants who plan to receive licensed vaccines or allergy treatments should be counseled to avoid scheduling receipt of these substances, when possible, within the 2 week interval after study product administration. To avoid unnecessary delays in study product administration, participants should be counseled to avoid scheduling receipt of these substances before study product administration (see Section 5.2.1).

Symptom diaries: Participants are asked to record symptoms on a daily basis using an electronic participant diary (paper alternative is available). All participants will be given a thermometer for oral temperature measurement and a ruler, and will be provided access to the electronic diary (paper alternative available). All participants will be provided training on diary completion, proper thermometer usage, and how to use of the measuring device to measure any injection-site induration and/or erythema. Participants will use the diary to record daily their highest temperature as well as local and systemic signs and symptoms. For Groups 1 and 2, symptoms are recorded for the day of vaccination and for 7 full days following each vaccination. For Group 3 only, symptoms are recorded for the day of vaccination, for 7 full days following the first two vaccinations, and for 14 full days following the third and fourth vaccinations. Participant diaries will be reviewed by a clinician and reconciled for accuracy and completeness. Attribution assessment will be performed and recorded on a case report form (CRF) for systemic reactogenicity events reported in the participant diary after additional evaluation of the participant by clinician. Clinicians may photograph the injection site in order to document injection-site reactogenicity.

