10.2 List of Participant Listings

These participant listings are included in the SMB reports:

- Discontinuation Status
- Pregnancies
- Severe or Life-Threatening Local and Systemic Reactogenicities
- Moderate Erythema and Induration
- Expedited Adverse Experiences (EAEs)
- Adverse Experiences of Special Interest (AESIs)
- Severe, Life-Threatening, or Fatal Adverse Experiences
- Adverse Experiences with Relationship to Study Product

- HIV Infection Results from Lab and Reported by Site
- Study Product Administration Errors
- Device Related Adverse Events

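### As printed, an injection-site erythema or induration of exactly 5 cm falls between Grade 1 and Grade 2

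*Protocol*

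**What the plan says.** Protocol Section 9.1 sets the general rule: "AEs will be graded according to the DAIDS Table for Grading the Severity of Adult and Pediatric Adverse Events, Corrected Version 2.1". It then lists exceptions. The one for injection-site erythema or redness and induration or swelling says that grading "will not consider surface area and interference with usual social and functional activities, such that" and goes on to define the grades by diameter:

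- The mildest category is given as "Grade 1 is: 2.5 to < 5 cm in diameter".
- The moderate category follows as "Grade 2 is: > 5 to < 10 cm in diameter".
- The severe category adds criteria other than size: "Grade 3 is: ≥ 10 cm in diameter OR ulceration OR secondary infection OR phlebitis OR sterile abscess OR drainage".

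The highest category depends on a potential threat to life, with no size criterion.

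The grades are used in three places:

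- **Tables.** Protocol Section 6.4.3 and SAP Section 9.2 tabulate each reactogenicity sign by severity. Each participant is counted once, at maximum severity.
- **SMB listing.** SAP Section 10.2 includes a listing titled "Moderate Erythema and Induration".
- **Clinical follow-up.** Protocol Section 8.3 states: "Any postvaccination reaction that is Grade 2 or higher will be assessed by a clinician within 48 hours after onset". Reactions that are improving or have resolved are exempt.

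Under Protocol Section 8.3, participants receive a ruler and are trained in "how to use of the measuring device to measure any injection-site induration and/or erythema". Neither document gives a reading precision or a rounding rule.

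**The concern.** A grading scale should give every diameter in its range one grade. Here the upper limit of Grade 1 and the lower limit of Grade 2 are both strict inequalities at the same number, so that number belongs to neither. It is the cut point between mild and moderate, and a ruler reading of exactly 5 cm is plausible.

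At stake is consistency. If the rule is silent, a site, a diary algorithm or an analysis programmer has to decide, and two of them could defensibly decide differently. The same decision determines whether the reaction enters the SMB's moderate listing and whether the 48-hour clinician assessment is formally due. Erythema and swelling or induration are listed among the common risks in Protocol Table 2-3, so the scale will be used.

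**Working it through.** The plan has no figure to reproduce. The check is whether the printed ranges cover every diameter d once.

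**Inputs (Protocol Section 9.1), size criteria only**

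- Grade 1: 2.5 ≤ d < 5
- Grade 2: 5 < d < 10
- Grade 3: d ≥ 10

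**Coverage.** [2.5, 5) ∪ (5, 10) ∪ [10, ∞) is every diameter from 2.5 cm upward except d = 5. No diameter falls in two ranges.

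| Diameter (cm) | Grade as printed |
|---|---|
| 2.5 | 1 |
| 4.9 | 1 |
| 5.0 | none |
| 5.1 | 2 |
| 9.9 | 2 |
| 10 | 3 |

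**Reading precision.** At each precision, exactly one mark between 2.5 and 10 cm has no grade:

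- whole centimetres, 3 to 9: (9 − 3)/1 + 1 = 7 marks, 1 ungraded
- half centimetres, 2.5 to 9.5: (9.5 − 2.5)/0.5 + 1 = 15 marks, 1 ungraded
- millimetres, 2.5 to 9.9: (9.9 − 2.5)/0.1 + 1 = 75 marks, 1 ungraded

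These count marks on a ruler. They do not estimate how often a reaction measures 5 cm.

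**Coverage if 5 cm is closed into one neighbour.** Tested with 5 ≤ d < 10 for Grade 2, the ranges cover every d ≥ 2.5 once. Closing Grade 1 at d ≤ 5 would cover it equally well. Coverage alone does not decide between them.

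**Effect on the outputs**

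- *Maximum-severity tables.* A participant with readings of 5.0 and 5.1 cm is Grade 2 whatever happens to the 5.0. A participant with 4.9 and 5.0 cm is affected: a program that skips ungraded values returns Grade 1, and one that treats 5 as moderate returns Grade 2. So the gap matters only when 5 cm is the largest reading and no non-size criterion (ulceration, drainage and so on) sets a higher grade.
- *Weight of one participant.* In Group 1, 1/9 = 11.1 percentage points. In Group 2 or Group 3, 1/18 = 5.6 percentage points. This is the shift if one participant is affected, not a forecast that one will be.
- *Discontinuation and pause rules.* Protocol Section 5.2.2 acts on related AEs at Grade 3 or 4. Table 9-1 acts on related AEs at Grade 3 or 4 and on related SAEs, where Grades 1, 2 and 3 lead to the same action. Neither uses the Grade 1/2 boundary.

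**The case against.** The strongest reply has three parts.

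1. **The gap may be settled elsewhere.** The scale is an exception to the DAIDS table, and the exception is worded as dropping surface area and functional interference. The base table may therefore still fix the 5 cm boundary, or the study-specific procedures may. Neither text is in the protocol or SAP. This stands as a reason to reconcile, not to assume an answer: Section 9.1 spells out each grade and states no fallback for 5 cm.
2. **The sign may be a conversion artefact.** A ≥ that lost its lower bar when the PDF became text would give exactly this wording. The intact ≥ in the Grade 3 line makes that less likely but does not exclude it.
3. **Care does not hang on the grade alone.** Under Protocol Section 8.3, staff contact each participant on the third or fourth day, a clinician reviews the diaries, and clinical judgment can prompt a visit at any grade. This stands.

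A reader might infer more than the documents support:

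- *That 5 cm readings will be common.* No diameter distribution or rounding practice is given.
- *That such reactions cannot be tabulated or are lost.* The diameter is still recorded; only its severity category is undefined.
- *That primary endpoint 1a is defective.* That endpoint is the collected reactogenicity signs and symptoms. Maximum severity is a tabulation rule, and a 5 cm reaction remains a collected sign.

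**Conclusion.** The gap is real on the printed text: 5 cm, and no other diameter from 2.5 cm upward, lacks a grade. It leaves the severity category undefined for a participant whose maximum is exactly 5 cm. Read literally, it also keeps that reaction outside the moderate listing and the Grade 2 condition for 48-hour assessment.

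The effect is probably small. It needs a maximum of exactly 5 cm, the documents give no frequency for that, and pause and discontinuation decisions are untouched. The 2.5 and 10 cm cut points are each assigned once and no reason is given for treating 5 cm differently, so this looks like a slip.

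The conclusion assumes that the source PDF prints > and that no document outside the protocol and SAP already assigns 5 cm.

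**What to change.** 1. Check the source PDF of Section 9.1 for a lost ≥ in the Grade 2 line.
2. If the sign is as printed, reconcile the boundary with the base DAIDS table so that 5 cm belongs to exactly one grade. Following the scale's own pattern at 2.5 and 10 cm (lower limit included, upper limit excluded), Grade 2 would read ≥ 5 to < 10 cm. The assignment is the sponsor's to confirm, because it also governs the 48-hour assessment.
3. Use that single definition in the diary/CRF grade derivation, the SAP reactogenicity tables and the SMB listing of moderate erythema and induration. Settle it before the analyses are run.

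The cost is one clarification, for which Protocol Appendix K already provides memos. Depending on the assignment, the count of moderate reactions may come out slightly higher or lower than under whatever ad hoc handling would otherwise apply.
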